4.5.1 Primary Efficacy Endpoint

Time to onset of CDP for at least 12 weeks (12-week CDP) during the double-blind treatment period

Significance Level

The null hypothesis will be tested at the $\alpha=0.05$ level (two sided test).

The hypotheses to be tested are:

- H0 (null hypothesis): There is no difference in the time to onset of CDP between the ocrelizumab and placebo groups.
- H1 (alternative hypothesis): There is a difference in the time to onset of CDP between the ocrelizumab and placebo groups.

Definition

The time to onset of CDP (12 week confirmation [days]) is defined as the time from baseline to the onset of the first disability progression that is confirmed at the next regularly scheduled visit ≥ 12 weeks after the initial disability progression. If the patient has an infection, dosing may not occur on the Day 1 visit. Baseline for the time to onset of confirmed disability is the date of randomization, independent of the date of first dosing. For example, a subject with delayed dosing may receive the first dose 2 weeks after the baseline visit; if an EDSS score is recorded between the randomization date and the date of the first dose, this value will be considered for the date of initial disability progression. Disability progression is defined as an increase of ≥ 1.0 point from baseline EDSS score if the baseline EDSS value is ≤ 5.5 points (inclusive) or an increase of ≥ 0.5 points if the baseline EDSS value is > 5.5 points. Assessments within 30 days after a protocol defined relapse will not be used for confirmation of CDP. The non-confirmatory EDSS assessments (between the initial disability progression and the confirmation of disability progression should also fulfill the requirements of the progression (see Section 2.1.1). Otherwise, the initial disability progression is not confirmed.

The baseline EDSS value is the average score of the EDSS assessment at screening and baseline (Day 1 visit) up to and including the date of randomization. If one of the values is missing, the non-missing values will be used as baseline.

An independent examining investigator at each study site will assess EDSS for all patients at the site at screening, baseline, every 12 weeks (regularly scheduled visit) during the blinded treatment period of the study, during the SFU period, at any unscheduled visits, and at withdrawal from treatment and end of study visits. Additional EDSS assessments for individual patients may be requested between visits (i.e., during an MS relapse).

The examining investigator is not the physician responsible for the patient care (the treating investigator).

The EDSS is based on a standard neurological examination; the seven categories of the EDSS representing FS (pyramidal, cerebellar, brainstem, sensory, bowel and bladder, visual, and cerebral [or mental], plus "other") are rated and scored (collectively, FSs), in addition to an ambulation score (0–12). Each domain of the FS is an ordinal clinical rating scale from 0 to 5 or 6. These ratings are then used in conjunction with observations and information regarding ambulation and the use of assistive devices (which will also be scored) to determine the EDSS score. The EDSS is a disability scale that ranges in 0.5point steps from 0 (normal) to 10.0 (death).

Analysis Methods

The ITT population analysis will be presented.

Patients who did not have initial disability progression at the time of primary database lock, time of early discontinuation, or loss to follow-up will be censored at the date of their last EDSS assessment that occurred during the treatment period.

There are various options to obtain EDSS assessments (confirmatory and non-confirmatory) and to record how the discontinuation from treatment and study can influence the confirmation of the disability progression. The following rules apply for all patients with initial disability progression:

- Initial disability progression must occur when the patient is still on treatment.
- All non-confirmatory EDSS assessments (if any) after initial disability progression and up to and including the confirmatory EDSS assessment should also fulfill the requirements of the progression as defined above. Otherwise an initial disability progression event cannot be confirmed.

Patients who experience initial disability progression will be treated as described in [Table 2](#)).

Table 2 Censoring Algorithm of Patients after Initial Disability Progression

Availability of EDSS Assessment for Patient with Initial Disability Progression	Recorded Disability Progression Status
Scenario A: Confirmatory EDSS assessment on treatment or after withdrawal from treatment	Confirmed disability progression
Scenario B: No confirmatory EDSS assessment; patient on treatment at the time of primary database lock	Censored at last EDSS assessment
Scenario C: Discontinues from treatment and is lost to follow-up; i.e., no available EDSS assessment at ≥ 84 days after initial disability progression	Confirmed disability progression

EDSS=Expanded Disability Status Scale.

The time to onset of CDP for the ocrelizumab arm and the placebo arm will be compared using a two-sided log-rank test stratified by geographic region (U.S. vs. ROW) and age (≤ 45 vs. > 45 years). The proportion of patients with CDP at predefined timepoints (i.e., 48 weeks, 96 weeks, etc.) will be estimated using Kaplan-Meier methodology. The overall hazard ratio will be estimated using a stratified Cox regression model with the same stratification factors used in the aforementioned stratified log-rank test.

Sample SAS code can be found below (SAS code is regarded as “draft” until fully validated at the analysis stage):

```
* Log-rank test;
proc lifetest data=CDP12;
  time CDP12TIME*CNSR(1);
  strata REGION AGE45 / group=ARMCD;
  ods output HomTests =_logrank;
run;

* Cox regression model;
proc phreg data=CDP12;
  class ARMCD / descending;
  model CDP12TIME*CNSR(1) = ARMCD / rl;
  strata REGION AGE45;
  ods output ParameterEstimates=est;
run;
```

Extension periods

This analysis will be repeated to include the EDSS assessments performed during the ECP and OLE periods for ECP and the combined double blind (DB)+OLE periods, with the same baseline as for the analysis during DB. Analysis containing only data from OLE will be performed considering the OLE baseline.

Patients discontinuing from either treatment periods (ECP or OLE) after initial disability progression and without confirmatory EDSS assessment will be imputed.

For the OLE period, initial disability progression has to occur while the patient is on OLE treatment. Confirmation of progression could occur at scheduled OLE or SFU visits after the OLE.

The same principle applies to all time to CDP endpoints below.

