5.11.1.1 Assessment of Disability

Disability in MS is commonly measured by the EDSS. The EDSS will be assessed in all participants by the independent Examining Investigator at screening, baseline, and every 12 weeks (regularly scheduled visit) during the blinded treatment period of the study, during the safety follow-up period, at any unscheduled visit, and at the withdrawal from treatment and end of study visits. As noted above, additional EDSS assessments for individual participants may be requested between visits (i.e., during an MS relapse, neurological worsening, etc.).

Disability progression is defined as an increase of ≥ 1.0 point from the baseline EDSS score that is not attributable to another etiology (e.g., fever, concurrent illness, or concomitant medication) when the baseline score is 5.5 or less, and ≥ 0.5 when the baseline score is above 5.5. Disability progression is considered confirmed when the increase in the EDSS is confirmed at a regularly scheduled visit at least 12 weeks after the initial documentation of the progression. An alternative definition of confirmed disability progression requires that the increase in EDSS be confirmed at least 24 weeks after the initial documentation of the progression. The initial event of disability progression must occur during the blinded treatment period.

The EDSS is based on a standard neurological examination, incorporating seven functional systems (pyramidal, cerebellar, brainstem, sensory, bowel and bladder, visual, and cerebral [or mental], plus "other") rated and scored as FSS. Each FSS is an ordinal clinical rating scale ranging from 0–5 or 6. In addition, there is an ambulation score ranging from 0–12. These ratings are then used in conjunction with observations and information concerning ambulation and use of assistive devices to determine the EDSS score. The EDSS is a disability scale that ranges in 0.5-point steps from 0 (normal) to 10 (death).

The MSFCS consists of 3 subscales, including the 9-HPT, PASAT, and T25FWT, which provide a global quantitative estimate of MS disability progression (Fischer et al. 1999; Frohman et al. 2008;). The MSFCS should be performed by the Examining Investigator or a qualified designee who must remain blinded to the treatment assignment.

5.11.2 **Brain MRI Imaging**

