- The m complete data sets are analyzed using standard statistical analyses.
- The results from the m complete data sets are combined to produce inferential results.

Fifty percent of the patients who had initial disability progression and then discontinued the treatment with no confirmatory EDSS assessments will be randomly assigned to have an event at the time of their initial disability progression; the other 50% of these patients will be censored at their last EDSS assessment, under the assumption that 50% of the patients with initial disability progression will later be confirmed at 12 weeks. A total of 1000 (m=1000) imputed datasets will be produced. The primary model described in Section 4.5.1 will be applied to each of the imputed datasets. Each imputed dataset will produce an estimate of the difference between ocrelizumab and placebo. The multiple imputation estimator of the difference between ocrelizumab and placebo is the average of the individual 1000 estimators. The variance of the estimator is the combination of the between- and within-imputation variability ([Carpenter and Kenward 2007](#)).

The 50% confirmation rate for patients with initial disability progression was estimated on the basis of previous studies conducted in patients with PPMS ([Weinshenker et al. 1996](#); Olympus, Study U2786g, data available upon request).

3. A sensitivity analysis, in which the patients who had initial disability progression and then discontinued the treatment with no confirmatory EDSS assessments will be considered to not have CDP, will be performed for the ITT population. This sensitivity analysis assumes that all patients lost to follow up after initial disability progression events will not have reached CDP. Hence, it will give an estimate of the maximal effect of informative censoring on the parameter estimates.
4. The influence of early progression events on treatment effect will also be evaluated by omitting the EDSS assessments performed between randomization and the Week 12 visit (≤ 83 days after randomization) with use of the ITT population.

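### SAP 4.5.1 gives two conflicting rules, with no stated precedence, for a patient whose initial progression is seen to reverse before day 84 and who discontinues with no later EDSS

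*SAP*

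**What the plan says.** SAP 4.5.1 states the persistence requirement twice. The endpoint definition says that EDSS values between the initial progression and its confirmation must also meet the progression criterion: "Otherwise, the initial disability progression is not confirmed". The Analysis Methods text repeats it in bullets introduced by "The following rules apply for all patients with initial disability progression", ending "Otherwise an initial disability progression event cannot be confirmed".

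The text after those bullets reads "Patients who experience initial disability progression will be treated as described in" Table 2. Scenario C of that table is "Discontinues from treatment and is lost to follow-up; i.e., no available EDSS assessment at ≥ 84 days after initial disability progression", and its recorded status is confirmed disability progression. The only test is whether an EDSS exists at 84 days or later.

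Protocol 8.2.1 also requires intervening values to stay at the progression level. It then counts as confirmed any participant who progresses, discontinues treatment early and has no confirmatory EDSS. It makes no exception for an observed reversal.

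Both documents schedule an EDSS when treatment stops: the protocol in 5.11.1.1 ("at any unscheduled visit, and at the withdrawal from treatment and end of study visits") and the SAP in 4.5.1 ("at any unscheduled visits, and at withdrawal from treatment and end of study visits").

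SAP 4.5.4 has two relevant sensitivity analyses. Item 2 assigns events to "Fifty percent of the patients who had initial disability progression and then discontinued the treatment with no confirmatory EDSS assessments" and censors the rest. Item 3 treats all of these patients as having no confirmed progression.

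**The concern.** The two rules meet in one patient: on-treatment initial progression, discontinuation, an EDSS below the threshold before day 84, and no EDSS from day 84 on. The bullet says the progression is not confirmed. Table 2 says it is. Table 2 also has no row, and gives no censoring date, for a discontinuer whose progression was seen to reverse.

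At stake is who counts as an event in the primary endpoint. The 24-week endpoint is analysed as the primary (SAP 4.5.2.1), and SAP 4.5.1 extends the principle to all later time-to-progression endpoints. The longer confirmation windows (at least 161 days for 24 weeks, at least 329 days for 48 weeks) contain more 12-weekly visits, so they leave more room for a contradicting value before discontinuation.

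**Working it through.** **1. Both rules applied to one constructed patient.** Baseline EDSS is 4.0, so the threshold is 5.0. EDSS is 5.0 at day 169 and 4.0 at a withdrawal visit on day 211, with none later.
- Bullet rule: 4.0 − 4.0 = 0, below the required 1.0, so the progression cannot be confirmed.
- Scenario C: 211 − 169 = 42 days and nothing at 84 days or more, so confirmed progression.

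The results are opposite.

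**2. Can the case arise?** Yes. An EDSS is due at the withdrawal visit. A regular visit can also fall short of 84 days: in Protocol Table 1 the visits on day 169 (±2) and day 253 (±4) can be 84 − 2 − 4 = 78 days apart.

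**3. The plan's own event figure.** Inputs from SAP 2.2: 2-year progression 43% on placebo and 30% on ocrelizumab, dropout 20% over 2 years, 2:1 allocation, N = 630, 1-year accrual, 3.5-year maximum.
- Hazards per year: placebo −ln(0.57)/2 = 0.2811; ocrelizumab −ln(0.70)/2 = 0.1783; ratio 0.6345. Dropout η = −ln(0.80)/2 = 0.1116.
- Event probability with follow-up uniform on 2.5 to 3.5 years, s = λ + η: (λ/s)·[1 − (e^(−2.5s) − e^(−3.5s))/s].
- Expected events: 149.7 + 103.7 = 253.5, against 253 stated. With N = 732 the result is 294.5, against 295 stated.
- Power = Φ(√(d·(2/3)·(1/3))·|ln HR| − z). With d = 253 it is 79.8% at alpha 0.01 and 92.7% at 0.05.

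The planning figures reproduce. The rule conflict does not affect them.

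**4. Rough size (assumption-based).** The documents give no count of Scenario C events, so this is an order of magnitude only.
- Primary events: 256 (SAP 1). With the 50% confirmation rate in SAP 4.5.4 item 2, initial progressions ≈ 256/0.5 = 512.
- Probability of dropout within 84 days: 1 − e^(−0.1116 × 84/365.25) = 2.5%.
- Discontinuing before confirmation: 512 × 0.0253 ≈ 13, of which about half, 6.5, would not have been sustained.
- If 25% to 100% of those show the reversal on an EDSS before day 84 and have none later (assumed): 1.6 to 6.5, or about 2 to 7 patients, 0.8% to 2.7% of 256.

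The figure scales with the dropout rate after a progression, which is not given. Safety follow-up EDSS visits would lower it.

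**5. Consequence at that size.**
- Power with 253 − 2 = 251 events: 79.4% at alpha 0.01 and 92.5% at 0.05. With 253 − 7 = 246: 78.5% and 92.0%.
- If 7 of 256 events were unrelated to treatment and the rest followed HR 0.635, a log-HR-weighted approximation gives exp[(1 − 7/256) × ln 0.635] = 0.643.

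**The case against.** The strongest reply is that the passages can be read together. The bullets are addressed to every patient with initial progression and come before Table 2. The table's first column is about which EDSS assessments are available, and Scenario C speaks of loss to follow-up. On that reading Scenario C is a missing-data rule, and an observed reversal fails the bullet before the table is reached. This is a fair reading, but the SAP does not state it. The bullet also runs up to the confirmatory assessment, which a Scenario C patient does not have, so a programmer could take it as not reaching that patient. Protocol 8.2.1 does not settle the matter.

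Second, item 3 of SAP 4.5.4 makes every disputed patient a non-event, so the influence on the primary result is already bounded. That stands. However, items 2 and 3 both pool patients seen to recover with patients who have no further EDSS, so neither isolates the issue.

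Third, the case is narrow. Discontinuers are meant to enter safety follow-up with further EDSS assessments (Protocol Table 3), and one at 84 days or later takes the patient out of Scenario C. A withdrawal EDSS may also itself be the initial progression. This stands. A reader might infer from the scheduled withdrawal visit that most discontinuers have an EDSS between progression and day 84; the documents show only that they can have one.

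**Conclusion.** The conflict is in the text and should be resolved. It is a contradiction between two stated rules with no order of precedence, limited to discontinuers with on-treatment initial progression, a below-threshold EDSS before day 84 and none from day 84 on. On planning rates, the 50% confirmation assumption and an assumed 25% to 100% observed-reversal share, about 2 to 7 events are affected. The true number is not in the documents and is probably a few at most.

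A reader might go further and infer that the reported primary analysis counted resolved progressions as events, or that the hazard ratio is biased toward 1. The documents support neither. They do not say which rule was programmed. Movement toward 1 holds only if the affected events are unrelated to treatment; the actual direction depends on their split by arm. The primary result is unlikely to turn on this.

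**What to change.** **Scenario C.** Restrict it to discontinuers with no EDSS at 84 days or later (or the matching window for 24- and 48-week progression) whose every available EDSS between the initial progression and the last assessment meets the threshold.

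**Discontinuers with a below-threshold EDSS before any confirmation.** State that this initial progression is not confirmed, that any later qualifying on-treatment progression is assessed in its own right, and that otherwise the patient is censored at the last on-treatment EDSS. State that Scenario A patients are unaffected, so that a fall in EDSS after confirmation does not undo an event.

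**Sensitivity item 2.** Limit the 50% imputation to the amended Scenario C.

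**Where to apply it.** Use the amended rule in the extension analyses for the final report, which SAP 2.3 lists as planned. The primary analysis is complete and unblinded, so its endpoint should not be redefined. Instead, report Scenario C events by arm, split by whether a reversal was on file, and add a sensitivity analysis that removes the observed reversals.

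**Cost.** A few lines of SAP text, a small change to the derivation, one table and one extra run. The downside is possibly a few fewer events.

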4.5.2 Secondary Efficacy Endpoints

The following secondary efficacy endpoints will be tested in the same hierarchical order listed here, if the primary endpoint and each preceding endpoint have reached the significance level of 0.05.

4.5.2.1 Time to Onset of Confirmed Disability Progression Confirmed for ≥ 24 Weeks

In addition to the primary analysis, the time to onset of CDP will be analyzed in the ocrelizumab and placebo treatment arms with use of a 24 week confirmation window for disability progression. The analysis of EDSS progression will be conducted as described for the primary analysis, with the exception that the time to onset of CDP (24 week confirmation) is defined as the time from baseline to the first disability progression that is confirmed at the next regularly scheduled visit ≥ 24 weeks (≥ 161 days) after the initial disability progression.

Extension Periods

This analysis will be repeated to include the EDSS assessments performed during the ECP and OLE periods for ECP and the combined DB+OLE periods, with the same baseline as for the analysis during DB. Analysis containing only data from OLE will be performed considering the OLE baseline.

4.5.2.2 Change in 25-Foot Timed Walk from Baseline to Week 120

The 25-foot timed walk is one of the three primary measures in an Multiple Sclerosis Functional Composite Scale (MSFCS) score and is the mean time from the two trials performed on the same visit. Detailed description on the derivation of the MSFCS score can be found in the MSFC Administration and Scoring Manual ([Fischer 2002](#)).

If the test results are not available due to a “physical limitation,” the maximum possible value for the scale (180 seconds) will be imputed. If one of the two trials is not available and not missing due to a “physical limitation,” the result from the other trial will be used to impute the missing value.

For outliers, the following rules will be applied. Values outside the lower and upper bounds will be treated as missing, and the imputation rule will be applied as defined above. The lower bound is 2.2 seconds ([Bohannon 1997](#)), and the upper bound is 180 seconds, according to the MSFCS Manual.

For the assessment of differences in the change in the 25-foot timed walk from baseline up to Week 120, a nonparametric ranked analysis of covariance (ANCOVA) will be

performed, with the ranked percent change in the 25-foot timed walk as the outcome variable and the ranked baseline value as the covariate, adjusting for geographical region (U.S. vs. ROW) and age (≤ 45 vs. > 45 years).

The last-observed value available before treatment discontinuation will be carried forward to impute the missing values. The baseline value will be carried forward for patients who did not have evaluable post-baseline observations. Patients with missing baseline value will be excluded from the analysis.

In order to obtain estimates of the treatment effect, a Mixed-Effect Model Repeated Measures (MMRM) analysis will be used. This model does not use the last observation carried forward (LOCF) method. The MMRM analysis incorporates post-randomization data collected at scheduled visits up to 120 weeks of treatment, and it will be used to assess all data collected over time, with consideration of the variance–covariance matrix of the repeated measures. This method allows for inclusion of data from patients with incomplete data from some scheduled timepoints.

The model will be implemented in SAS using PROC MIXED and will include the log transformed ratio of post-baseline timepoints to baseline in the 25-foot timed walk at each visit as the dependent variable. The fixed effects in the model will include independent variables of randomized treatment, visit (nominal post baseline visits as per the Schedule of Assessments), baseline-by-visit interaction and treatment-by-visit interaction, along with the following baseline covariates, log-transformed 25-foot timed walk at the baseline visit, geographical region (U.S. vs. ROW), and age (≤ 45 vs. > 45). Visit will be treated as a repeated variable within a patient. Patient, treatment and visit will be treated as factor variables. An unstructured variance–covariance structure will be applied to model the within-patient errors. The Restricted Maximum Likelihood (REML) method will be used for estimates of variance components. Denominator degrees of freedom will be estimated using Satterthwaite's approximation.

To estimate the difference between the ocrelizumab and placebo groups in change from baseline to Week 120, a treatment-by-visit interaction contrast will be constructed (i.e., the treatment group contrast at Week 120). On the basis of this analysis, back transformed estimates of least square means and the 95% confidence interval (CI) for the ratio of 25-foot timed walk at each visit relative to the baseline will be reported.

Graphical presentations for least square means and 95% CIs will be used to illustrate trends over time.

Sample SAS code can be found below (SAS code is regarded as “draft” until fully validated at the analysis stage):

```
*ranked ANCOVA;
  proc sort data=MSFC_locf out=ancova;
    by REGION AGE45;
  run;

  proc rank data=ancova out=ranks;
    by REGION AGE45 ;
    var lbfwt lcfwt;
  run;

  proc reg data=ranks;
    by REGION AGE45;
    model lcfwt=lbfwt ;
    output out=residual r=reside;
    quit;

  proc freq data=residual noprint ;
    tables region*AGE45*ARMCD*reside/cmh2 scores=modridit;
  run;

*MMRM;
  proc mixed data=MSFC method=REML;
    class REGION AGE45 ARMCD VISIT USUBJID;
    model log(AVG25F/BASE) = log(BASE) REGION
    AGE45 ARMCD VISIT log(BASE)*VISIT ARMCD*VISIT /
    ddfm= satterthwaite;
    repeated VISIT / type=un subject = USUBJID;
    lsmeans ARMCD*VISIT / pdiff cl;
    ods output lsmeans = lsm; * contains the adjusted means;
    ods output difs = dif; * contains treatment differences;
  run;
```

Extension Periods

This analysis will be modified to include data collected during the ECP and OLE periods. Change from baseline during ECP, change from baseline until the last mature visit during the combined ECP+OLE periods and change from OLE baseline until the last mature visit during the OLE period will be analyzed. The last mature visit is defined as the visit where the majority of patients have completed prior to the data cutoff date.

The model will include the 1/x transformed value of the 25-foot timed walk at each visit as the dependent variable, instead of the log-transformation applied previously.

For the combined ECP and OLE periods, visits will be backdated in order to have continuous time visits post ECP. Below algorithm will be considered for backdated OLE visits.

Backdate Algorithm (continuous OLE visits):

- All scheduled OLE labeled visits to be windowed to the nearest 12-week visit following the scheduled visits during the ECP.

- For each OLE patient, create an artificial Schedule of Assessment (SoA): a visit every 12 weeks in continuation to the ECP.
- Assign a new visit label from the closest visit from artificial SoA to OLE visit.
- All OLE Week yy visits to be replaced by Week xx, in continuation to the visit labels during the ECP.
- Use the new visit labels (no OLE Week yy visit label) for the analysis purpose.
- If multiple OLE visits are windowed to the same 12 week visit, then the latest chronological visit will be used for the analyses.

4.5.2.3 Change in Total Volume of T2 Lesions on MRI Scans of the Brain from Baseline to Week 120

For the assessment of differences in the percent change in total volume of T2 lesions from baseline up to Week 120, ranked ANCOVA and MMRM analyses will be undertaken using the same approach as described above in Section 4.5.2.2, except that the baseline covariate for the MMRM will be baseline log-transformed T2 lesion volume, geographical region (U.S. vs. ROW), and age (≤ 45 vs. >45 years).

T2 lesion volumes below the lower limit of quantification of 0.009 cm^3 (3 voxels) will be set to this limit.

Extension Periods

This analysis will be extended to include data collected during the OLE period. Ratio relative to baseline until the last mature visit during the combined ECP+OLE period and ratio relative to OLE baseline until the last mature visit during the OLE period will be analyzed. Note that no additional MRI assessments were performed between 120 weeks and OLE start, hence analysis for the ECP period is the same as that for the DB period.

4.5.2.4 Percent Change on MRI from Week 24 to Week 120 in Total Brain Volume

For the assessment of differences in the mean percentage change in brain volume on MRI scans from Week 24 to Week 120, an MMRM analysis will be undertaken using the same approach as described above in Section 4.5.2.2, except:

- The response variable will be the percentage change from Week 24 to subsequent visits (Weeks 48, and 120). Baseline brain volume data will not be a feature in this analysis.
- Covariates will be brain volume at Week 24, geographical region (U.S. vs. ROW), and age (≤ 45 vs. >45 years).

The choice of Week 24 as “baseline” in this analysis, rather than the baseline visit, is a widely accepted approach to establish a stable baseline and avoid the physiological effect of pseudo-atrophy.

Extension Periods

This analysis will be extended to include data collected during the OLE period. Percentage change from Week 24, baseline and OLE baseline until the last mature visit will be analyzed.

4.5.2.5 Change from Baseline in Quality of Life as Measured by the SF36 (Physical Component)

The SF-36v2 is a 36-item, self-reported, generic measure of quality of life that has been widely used in multiple disease areas. It is composed of eight health domains: Physical Functioning (PF), Role-Physical (RP), Bodily Pain (BP), General Health (GH), Vitality (VT), Social Functioning (SF), Role-Emotional (RE), and Mental Health (ME). Based on these domain scores, the Physical Component Summary (PCS) Score and the Mental Component Summary (MCS) Score will be computed. The standard form of the instrument, with a 4-week recall, is being administered in the studies.

Scoring and rules for missing items will follow the SF-36v2 User's Manual. In brief, scoring for each health domain scale involves (a) recoding item response values, (b) summing recoded response values for all items in a given scale to obtain the scale raw score, and (c) transforming the scale raw score to a 0–100 score. The PCS score is computed by (a) multiplying each health domain z score by a scale-specific physical factor score coefficient, (b) summing the resulting products, and (c) converting the product total to a T score. The MCS score is computed in the same manner, instead using scale-specific mental factor score coefficients.

For the assessment of differences in the mean change in PCS score from baseline up to Week 120, MMRM analyses will be undertaken using the same approach as described above in Section 4.5.2.2, except baseline covariates here will be as follows: baseline PCS score, geographical region (U.S. vs. ROW) and age (≤ 45 years, > 45 years).

Extension Periods

Additional data from the OLE period will be descriptively analyzed. Note that no additional SF-36 assessments were performed between 120 weeks and OLE start.

